3.3. Other Endpoint(s)

3.3.1. Urine PK Parameters: CL_r, Ae₂₄, Ae₂₄%

Urine samples for PK analysis will be collected according to the Schedule of Activities given in the protocol. The urine PK parameters in Table 6 will be determined:

Table 6. Summary of Urine PK Parameters to be calculated

Parameter	Analysis Scale	PF-06882961 20mg
Ae ₂₄	ln	D
Ae ₂₄ %	ln	D
CL _r	ln	A, D

Abbreviations: A = analyzed using a statistical model; D=displayed with descriptive statistics as outlined in Section 6.3.1; R=raw (untransformed); ln=natural-log transformed

3.3.2. Coproporphyrin I (CP-I) concentration

Plasma CP-I concentrations will be collected prior to dosing on Day 1 only.

3.4. Baseline Variables

Not applicable.

3.5. Safety Endpoints

See Section 3.2.2.

4. ANALYSIS SETS (POPULATIONS FOR ANALYSIS)

Data for all participants will be assessed to determine if participants meet the criteria for inclusion in each analysis population prior to releasing the database and classifications will be documented per standard operating procedures.

Population	Description
Enrolled	All participants who sign the ICD
Evaluable	All participants assigned to IP and who take at least 1 dose of IP.
Safety	All participants assigned to IP and who take at least 1 dose of IP.
PK Concentration Set	The PK concentration population is defined as all participants who received at least 1 dose of PF-06882961 and in whom at least 1 plasma concentration value is reported.
PK Parameter Set	The PK parameter analysis population is defined as all participants who received at least 1 dose of PF-06882961 and have at least 1 of the plasma PK parameters of interest calculated.
Urine PK Concentration Set	The urine PK concentration population is defined as all participants who received at least 1 dose of PF-06882961 and in whom at least 1 urine concentration value is reported.
Urine PK Parameter Set	The urine PK parameter analysis population is defined as all participants who received at least 1 dose of PF-06882961 and have at least 1 of the urine PK parameters of interest calculated.
CP-I Concentration Set	The CP-I concentration population is defined as all participants who received at least 1 dose of PF-06882961 and in whom at least 1 CP-I concentration value is reported.

5. GENERAL METHODOLOGY AND CONVENTIONS

The following group labels (or similar) will be used for tables and figures unless otherwise stated:

Group	Description of Group	Label
1	Healthy and normal renal function	Healthy Normal
2	T2DM Normal renal function	T2DM Normal
3	T2DM Mild renal impairment	T2DM Mild RI
4	T2DM Moderate renal impairment	T2DM Moderate RI
5	T2DM Severe renal impairment	T2DM Severe RI

5.1. Hypotheses and Decision Rules

There is no statistical hypothesis testing planned for this study and no statistical decision rules will be applied.

5.2. General Methods

5.2.1. Analyses for Continuous Endpoints

Unless otherwise stated, continuous variables will be presented using summary statistics: number of observations, arithmetic mean, standard deviation, median, minimum and maximum values.

5.2.2. Analyses for Categorical Endpoints

Categorical variables will be presented using summary statistics: number of observations and percentages.

5.2.3. One-way Analysis of Variance (ANOVA)

The *ANOVA* model will include all groups (i.e. both T2DM and healthy participants from the 5 groups) as a factor.

Estimates of the adjusted mean differences (Test-Reference) and corresponding 90% CIs will be obtained from the model. The adjusted mean differences and 90% CIs for the differences will be exponentiated to provide estimates of the ratio of adjusted geometric means (Test/Reference) and corresponding 90% CIs. Example SAS code is given in [Appendix 1](#).

Potential differences in demographic characteristics between healthy (Group 1), T2DM normal (Group 2) and T2DM renal impairment function participants (Groups 3, 4, 5) and their impact on study conclusions will be explored based on consideration of the covariates weight, gender and age. This will be implemented by utilizing a stepwise linear regression approach, with model selection using Akaike's Information Criterion [AIC]). All the above covariates and factors will be considered (group as a factor will be restricted to always remain in the model) and if the final model selected includes at least one of these additional covariates/factors, this additional model will be reported in addition to the main ANOVA model above. Example SAS code is given in [Appendix 1](#).

5.2.4. Linear Regression

Linear regression analysis will include eGFR as the explanatory variable, based on eGFR values obtained on Day 1 and will include only participants from the T2DM groups (Groups 2 to 5). Estimates of the slope and intercept, together with their precision (90% CIs), and the coefficient of determination will be obtained from the model. Example SAS code is given in [Appendix 1](#).

Additionally, as an exploratory analysis, the effect of weight, gender and age will be explored as additional covariate/factors in the models, as appropriate. This will be implemented by utilizing a stepwise linear regression approach, with model selection using Akaike's Information Criterion [AIC]). All the above covariates and factors will be considered (eGFR will be restricted to always remain in the model) and if the final model selected includes at least one of these additional covariates/factors, this additional model will be reported in addition to the main linear regression above. Example SAS code is given in [Appendix 1](#).

5.3. Methods to Manage Missing Data.

For the analysis of safety endpoints, the sponsor data standard rules for imputation will be applied.

In all PK data presentations (except listings) and CP-I, concentrations below the limit of quantification (BLQ) will be set to zero. In listings BLQ values will be reported as “<LLQ”, where LLQ will be replaced with the value for the lower limit of quantification.

In PK summary tables and plots of median profiles, statistics will be calculated having set concentrations to missing if one of the following cases is true:

1. A concentration has been collected as ND (i.e. not done) or NS (i.e. no sample),
2. A deviation in sampling time is of sufficient concern or a concentration has been flagged anomalous by the pharmacokineticist.

Note that summary statistics will not be presented at a particular time point if more than 50% of the data are missing.

Participants who experience events that may affect their PK profile (e.g. lack of compliance with dosing or vomiting) may be excluded from the PK analysis. At the discretion of the pharmacokineticist, a concentration value may also be excluded if the deviation in sampling time is of sufficient concern or if the concentration is anomalous for any other reason.

A full list of protocol deviations will be compiled and reviewed to identify major and minor deviations prior to database closure.

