4. STUDY DESIGN

4.1. Overall Design

This Phase 1, open-label, single-dose, parallel group, multi-site study will assess the effect of varying degrees of renal impairment on the PK, safety and tolerability of PF-06882961 after a single oral dose of 20 mg administered in a fed state ([Section 5.3.1](#)).

Approximately 40 participants will be enrolled in the study. Refer to Table 1 below for details of study groups. Due to the potential difficulty in recruiting T2DM patients with estimated glomerular filtration rate (eGFR) <30 mL/min, the number of participants to be enrolled in this group is flexible (6 to 8 participants).

This study will permit enrollment of 2-4 participants on dialysis, as part of the severe renal impairment group, to assist in recruitment of patients with more advanced renal impairment and to permit assessment of the PK of PF-06882961 in participants with the highest degree of renal impairment. [CCI](#)

[CCI](#) dialysis is not expected to significantly impact the clearance of PF-06882961 and therefore the dialysis clearance of PF-06882961 will not be characterized in this study. Thus, Day 1 (per the [SoA](#)) will occur in dialysis patients on a day in which dialysis is not administered.

Table 1. Study Groups

Group	Disease State	Renal Impairment	No. of Participants	eGFR ^a (mL/min)
1	None (healthy)	None (Normal Renal Function)	8	≥90
2	T2DM	None (Normal Renal Function)	8	≥90
3	T2DM	Mild	8	60-89
4	T2DM	Moderate	8	30-59
5	T2DM	Severe	6-8 ^b	<30

a. Estimate of eGFR based on the SCr-based CKD-Epi equation. The eGFR will be multiplied by each participant's ratio of BSA/1.73 to obtain the BSA-unnormalized eGFR value. The average of the 2 unnormalized eGFR values from S1 and S2 will be used for study enrollment and group placement. Note: participants on dialysis will be placed in Group 5 regardless of unnormalized eGFR from S1 and S2.

b. This includes approximately 4 participants not on dialysis and 2-4 participants on dialysis.

Screening will occur within 28 days of the first dose of study intervention on Day 1. All participants will provide informed consent and undergo Screening evaluations to determine their eligibility. All participants who are not on dialysis must have stable renal function to enter the study, defined as ≤25% difference between 2 measurements of BSA-unnormalized eGFR obtained from the 2 screening visits, S1 and S2 as listed in the [SoA](#).

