5.1. Inclusion Criteria

5.1.1. Inclusion Criteria for All Participants

Participants are eligible to be included in the study only if all of the following criteria apply:

1. Stable renal function (for participants not on dialysis) defined as $\leq 25\%$ difference between 2 measurements of eGFR (as calculated by the sponsor-identified central laboratory using the CKD-EPI equation)¹ obtained at Screening visits S1 and S2. The average of the 2 eGFR values obtained from S1 and S2 will be used for study enrollment and assignment to appropriate renal function group (see [Table 1](#)). **Note:** participants on dialysis will be placed in Group 5 regardless of eGFR from S1 and S2 (S2 is optional for dialysis participants only).

Age and Sex:

2. Male and female participants must be ≥ 18 years of age, inclusive, at the time of signing the informed consent document (ICD).
 - Refer to [Appendix 4](#) for reproductive criteria for male ([Section 10.4.1](#)) and female ([Section 10.4.2](#)) participants.

Type of Participant and Disease Characteristics:

3. Participants who are willing and able to comply with all scheduled visits, treatment plan, laboratory tests, lifestyle considerations, and other study procedures, including the ability to perform self-monitoring blood glucose at a frequency deemed appropriate by the investigator.

Weight:

4. Body mass index (BMI) of $\geq 18.0 \text{ kg/m}^2$ and $<45.4 \text{ kg/m}^2$; and a total body weight $>50 \text{ kg}$ (110 lb).

Informed Consent:

5. Capable of giving signed informed consent as described in [Appendix 1 \(Section 10.1\)](#), which includes compliance with the requirements and restrictions listed in the ICD and in this protocol.

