5.1.3. Additional Inclusion Criteria for T2DM Participants with Normal Renal Function (Group 2)

1. A prior diagnosis of T2DM with an HbA1c $\geq 6\%$ and $\leq 10.5\%$, at Screening visit S1, confirmed by a single repeat, if deemed necessary.
2. Normal renal function (mean eGFR $\geq 90 \text{ mL/min}$) based on an average of measures from Screening visits S1 and S2.
3. See [Appendix 8](#) for details regarding prohibited prior/concomitant medications.
4. Demographically comparable to participants with impaired renal function:
 - a. A body weight within $\pm 15 \text{ kg}$ of the mean body weight of the pooled renal impairment groups (Groups 3, 4, and 5), as provided by sponsor;

- b. An age within ± 10 years of the mean age of the pooled renal impairment groups (Groups 3, 4, and 5), as provided by sponsor;
- c. Attempts will be made to ensure that the male to female distribution in Group 2 is comparable to that in the pooled renal impairment groups (Cohorts 3, 4, and 5).

5.1.4. Additional Inclusion Criteria for T2DM Participants with Impaired Renal Function (Groups 3-5)

1. A prior diagnosis of T2DM with an HbA1c $\geq 6\%$ and $\leq 10.5\%$, at Screening visit S1, confirmed by a single repeat, if deemed necessary.
2. Meet the eGFR criteria listed for Groups 3, 4, or 5 (for participants not on dialysis) in Table 1 based on an average of measures from Screening visits S1 and S2.
3. Stable concomitant medications, as defined in [Section 6.5](#), for the management of medical conditions relevant to an individual participant's medical history. Participants receiving fluctuating concomitant medications/treatments may be considered, on a case-by-case basis with input from sponsor, if the underlying disease is stable.
4. For Group 5 participants on dialysis **only**, participants must have required hemodialysis for at least 6 weeks and need dialysis sessions 3 times per week.

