9.4.3.1.3. Statistical Methods

Linear regression will be used to characterize the potential relationship between appropriate PK parameters (CL/F, CL_u/F and CL_r) for PF-06882961 and renal function (eGFR). eGFR values obtained on Day 1 and only participants from the T2DM groups (Groups 2 to 5) will be included in the regression analysis. Estimates of the slope and intercept, together with their precision (90% CIs), and the coefficient of determination will be obtained from the model. The effect of covariates such as weight, gender, and age may be explored, and details will be provided in the SAP.

A one-way analysis of variance (ANOVA) will be used to compare the natural log transformed AUC_{inf} (if data permit), AUC_{last}, C_{max}, fu, AUC_{inf,u} (if data permit), AUC_{last,u} and C_{max,u} of PF-06882961 for each of the T2DM renal impairment groups (Test, Groups 3, 4, 5) to the T2DM normal renal function group (Reference, Group 2). Also, the T2DM normal renal function group (Test, Group 2) will be compared to the healthy normal renal group (Reference, Group 1). The ANOVA model will include all groups (ie, both T2DM and healthy participants from the 5 groups). Estimates of the adjusted mean differences (Test-Reference) and corresponding 90% CIs will be obtained from the model. The adjusted mean differences and 90% CIs for the differences will be exponentiated to provide estimates of the ratio of adjusted geometric means (Test/Reference) and corresponding 90% CIs. If substantial differences in demographic characteristics between healthy (Group 1), T2DM normal (Group 2) and T2DM renal impairment function participants (Groups 3, 4, 5) are observed, covariates such as weight, gender, and age may be explored.

The PK parameters for PF-06882961 will also be summarized descriptively by renal function group and population (healthy vs. T2DM). Box and whisker plots for individual PK parameters (AUC_{inf}, AUC_{last}, C_{max}, fu, AUC_{inf,u}, AUC_{last,u} and C_{max,u}) will be constructed by renal function group and population and overlaid with geometric means.

For summary statistics and median or mean plots by sampling time, the nominal PK sampling time will be used. For individual participant plots by time, the actual PK sampling time will be used.

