6.1. Primary Endpoint(s)

6.1.1. C_{\max} , AUC_{inf} , AUC_{last} , fu for PF-06882961

6.1.1.1. Main Analysis

C_{\max} , AUC_{inf} (if data permit), AUC_{last} and fu will be listed, summarized descriptively and analyzed by group for participants in the PK parameter set (as defined in Section 4). Missing values will be handled as detailed in Section 5.3.1.

Linear regression will be used to characterize the potential relationship between appropriate PK parameters (CL/F , CL_u/F and CL_r) for PF-06882961 and renal function (eGFR as obtained on Day 1 and defined by the SCr-based CKD-Epi equation in Section 3.2.1), as described in Section 5.2.4, where the PK parameter will be the dependent variable in the separate models.

Plots of PK parameters (CL/F , CL_u/F and CL_r) for PF-06882961 versus renal function (eGFR as obtained on Day 1 and defined by the SCr-based CKD-Epi equation in Section 3.2.1) will be constructed. A regression line and 90% confidence region for the PK parameters and eGFR will be included if appropriate. Vertical lines for the renal function group cut-off values will also be presented on the plots. Different symbols will be used to identify participants from different renal function groups.

For exploratory purposes, these analyses and figures will additionally be carried out separately for each of the alternative two methods for calculating eGFR, as defined in Section 3.2.1.

A one-way analysis of variance (ANOVA) described in Section 5.2.3, that includes all 5 groups in the same model, will be used to compare the natural log transformed of C_{\max} , AUC_{inf} , AUC_{last} and fu of PF-06882961 separately, for each of the T2DM renal impairment groups (Test, Groups 3, 4, 5) to the T2DM normal renal function group (Reference, Group 2). Also, the T2DM normal renal function group (Test, Group 2) will be compared to the healthy normal renal group (Reference, Group 1).

For summary statistics and median or mean plots by sampling time, the nominal PK sampling time will be used. For individual participant plots by time, the actual PK sampling time will be used. The plasma PK parameters of PF-06882961 for each group will be summarized as specified in Table 7 below.

Table 7. Summary statistics to be produced for Plasma PK Parameters of PF-06882961

Parameter	Summary Statistics
-----------	--------------------

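### The clearance-on-eGFR regressions pool 2-4 dialysis participants with everyone else, unmarked and with no fit that leaves them out, so a dialysis-specific difference could read as a trend across the eGFR range

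*SAP*

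**What the plan says.** Both documents define the same regression. Protocol 9.4.3.1.3 states that "eGFR values obtained on Day 1 and only participants from the T2DM groups (Groups 2 to 5) will be included in the regression analysis". SAP 5.2.4 repeats this: the model is "based on eGFR values obtained on Day 1 and will include only participants from the T2DM groups (Groups 2 to 5"), and SAP 6.1.1.1 specifies the x-variable for fits and plots as "eGFR as obtained on Day 1 and defined by the SCr-based CKD-Epi equation in Section 3.2.1".

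On Group 5, a footnote to Table 1 in protocol 4.1 reads "This includes approximately 4 participants not on dialysis and 2-4 participants on dialysis". With 6-8 in that group and 8 in each of Groups 2-4, dialysis participants are 2 of 30 to 4 of 32 in the regression.

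Elsewhere the protocol sets these participants' eGFR aside:
- Grouping (4.1, Table 1): "participants on dialysis will be placed in Group 5 regardless of unnormalized eGFR from S1 and S2".
- Stability (5.1.1): the criterion begins "Stable renal function (for participants not on dialysis) defined as", so they are exempt from the 25% rule.
- Second screening visit: optional for them (Schedule of Activities, footnote a).
- Timing (4.1): Day 1 "will occur in dialysis patients on a day in which dialysis is not administered". No interval since the last session is fixed.
- Dialysis schedule (5.1.4): "participants must have required hemodialysis for at least 6 weeks and need dialysis sessions 3 times per week".

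Neither document removes them from the regression or gives them a different x-value. SAP 6.1.1.1 assigns plot symbols by renal function group only, and SAP 6.4 plans no subset analyses. The Cockcroft-Gault and MDRD reruns in SAP 3.2.1 and 6.1.1.1 also use serum creatinine.

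**The concern.** A value the protocol does not rely on to classify a dialysis participant becomes an exact continuous regressor for that participant. Serum creatinine in someone on haemodialysis is not at steady state and depends partly on the time since the last session. That is general clinical pharmacology and is not stated in the documents, but the exemptions above are consistent with it. Three sessions a week leave four non-dialysis days. On a usual alternating schedule (an assumption), three of those four directly follow a session.

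Two consequences need separating. One is error in x. The other is influence: these participants sit at the end of the x-range, and a straight line through Groups 2-5 spreads any difference particular to them over mild and moderate impairment as well. Protocol 4.2 gives altered non-renal clearance as the reason for a full-range design, and protocol 2.3 says the results will inform dosing recommendations. A reader should therefore be able to see whether the slope comes from the whole range or from 2-4 people.

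**Working it through.** **The plan's own precision figure.** Protocol 9.2 gives a half-width of ±0.490 for a between-group log difference (8 per group, SD 0.489, 90% CI, 80% coverage probability). t(0.95, 14) × 0.489 × √(2/8) × √(χ²(0.80, 14)/14) = 1.761 × 0.489 × 0.5 × √(18.15/14) = 0.490, so it reproduces. No precision is given for the regression.

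**Inputs.** SD 0.489 is the protocol's figure for ln AUCinf. It carries over to ln CL/F because the dose is fixed. The log scale follows SAP Tables 4-6 and the example code in SAP Appendix 1. The documents give no distribution of eGFR within groups, so two layouts are assumed, evenly spaced within groups:
- Layout B: 8 participants each over 92-130, 61-88 and 31-58, and 4 non-dialysis severe over 16-28.
- Layout A: 8 each over 90-120, 60-89 and 30-59, and 4 over 15-29.

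Each adds 2 or 4 dialysis participants at a common x.

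**Step 1: how far x can move.** Above κ, CKD-EPI varies as SCr^-1.209. For a man of 60 the printed equation gives 5.7 at SCr 9 mg/dL and 17.9 at 3.5 mL/min/1.73 m². An assumed 50-70% fall in creatinine over a session multiplies eGFR by (1/0.5)^1.209 = 2.3 to (1/0.3)^1.209 = 4.3. Dialysis participants can therefore land among the non-dialysis severe participants.

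**Step 2: what x-error alone does.** Suppose true function is 5 and CL/F changes 2-fold per 100 mL/min.
- Layout A, assigned x 10 / 15 / 20 / 29: slope overstated by 1.6 / 3.1 / 4.3 / 5.9% (2 on dialysis) or 2.6 / 5.1 / 7.2 / 10.2% (4 on dialysis).
- Worst case on the log scale: 0.102 × ln 2 = 0.071 per 100 mL/min, against a 90% half-width of 0.467. The 2.00-fold ratio becomes 2.15.

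**Step 3: leverage.** h = 1/n + (x − x̄)²/Sxx. Layout B, 4 at x = 5: 1/32 + (5 − 60.88)²/44,831 = 0.101. At x = 18 it is 0.081. With 2 it is 0.126 and 0.097. Layout A at x = 5 gives 0.105 (4) and 0.133 (2). The mean is 2/32 = 0.063 or 2/30 = 0.067.

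**Step 4: a dialysis-specific difference.** Assume CL/F is flat in the 28 others and 40% lower on dialysis. The fitted slope is ln(0.6) × Σ(x − x̄)/Sxx, summed over dialysis participants, and the fall from 110 to 15 is 1 − exp(−95 × slope). Layout B:

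| On dialysis | x | x̄ | Sxx | Slope | Fitted fall |
|---|---|---|---|---|---|
| 4 | 5 | 60.88 | 44,831 | 0.00255 | 21.5% |
| 4 | 18 | 62.50 | 39,611 | 0.00230 | 19.6% |
| 2 | 5 | 64.60 | 38,171 | 0.00160 | 14.1% |
| 2 | 18 | 65.47 | 35,387 | 0.00137 | 12.2% |

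With 4 on dialysis the line also shows a fall of 14-15% at eGFR 45 (1 − exp(−65 × slope)), where the scenario has none.

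**Step 5: precision around that.** With 4 at x = 5, the slope half-width is t(0.95, 30) × 0.489/√44,831 = 0.00392. The 90% interval is exp(−0.242 ± 95 × 0.00392), or −46% to +14%. It includes no effect.

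**Step 6: cost of omitting them.** Half-width per 100 mL/min:
- Layout B: 0.477 without, against 0.392 (4 at x = 5) to 0.442 (2 at x = 18), so 22% to 8% wider.
- Layout A: 0.513 without, against 0.415 (4 at x = 5) to 0.475 (2 at x = 20), so 24% to 8% wider.

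**The case against.** The strongest reply is that the x-values do not drive the distortion. Step 4 bears this out: the fitted fall is larger at x = 5, where a true low GFR would lie, than at x = 18. A perfectly measured GFR would not remove it. A reader might infer from the protocol's exemptions that the regression is invalidated by a bad explanatory variable. Step 2 does not support that.

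The 40% step is also hypothetical. SAP 2.2 expects dialysis to have little effect on clearance. That statement concerns removal by the procedure, not non-renal clearance in end-stage disease, so it neither predicts nor rules out the scenario. Lower CL/F in the participants with least function would be part of the renal effect under study. What is at issue is only whether it is shown where it occurs.

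The scope is limited, and this stands. The primary comparisons of Cmax, AUCinf, AUClast and fu are group ANOVAs without eGFR. No hypothesis test or decision rule depends on the slope. Anuric dialysis participants provide no urine and already drop out of the CLr fit.

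Finally, protocol 4.1 includes dialysis participants to cover the highest degree of impairment. Making the fit without them the main one would discard that end of the range and lose precision. The documents do not require that choice, and it is not recommended here.

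**Conclusion.** The gap is real and modest. All T2DM participants enter the regression, dialysis participants cannot be identified on the plots, and no alternative fit is planned. Error in their eGFR shifts the slope by about 0-10%, which is minor against its interval. Their influence matters more: 2-4 points can produce a fitted fall of 12-22% that belongs to them alone, under the assumed 40% difference, the assumed eGFR layout and the protocol's SD.

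A reader might go further and conclude that the trial would report a false renal trend or that its primary result is compromised. Neither follows, because the interval in that scenario includes no effect and the primary ANOVA does not use eGFR. The point concerns how the CL/F and CLu/F regressions can be interpreted. It applies to CLr only for dialysis participants who still pass urine.

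**What to change.** In SAP 5.2.4 and 6.1.1.1, pre-specify each regression of CL/F, CLu/F and CLr on eGFR twice, with and without dialysis participants, and report slope, intercept, R² and 90% intervals side by side. Give dialysis participants a distinct symbol on the plots. Amend SAP 6.4 so that this is allowed, and note the addition in protocol 9.4.3.1.3 at the next amendment.

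The cost is one extra model per parameter and no new data. The fit without dialysis participants has a slope interval about 8-24% wider and should not be read below the lowest non-dialysis eGFR. With so few dialysis participants, the pair of fits shows how far the slope depends on them. It will not establish a dialysis-specific effect. Specifying both before the data are seen avoids choosing between them afterwards.
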